## Aim

The purpose of this study is to investigate course of illness leading to reoperation after primary anti-reflux surgery and investigate the utilization of anti-reflux treatment, both medical and surgical, in the period 2000-2017

## Background

Episodic reflux of gastric contents to the esophagus is physiological but is considered gastroesophageal reflux disease (GERD) when accompanied by bothersome symptoms, typically heartburn, regurgitation or retrosternal pain. Extra-esophageal symptoms such as asthma, laryngitis and chronic cough may also occur (1). GERD is a complex and multifaceted disease (2, 3), affecting 10-20% of the Western population (4) and has been shown to significantly reduce the quality of life (5). Worldwide, the prevalence of GERD has been increasing (6-8). Treatment of GERD consists of anti-secretory drugs, mainly proton pump inhibitors (PPI), or anti-reflux surgery. Laparoscopic anti-reflux surgery is considered standard of care in surgical treatment of gastro-esophageal reflux disease (9) and with careful patient selection based on thorough preoperative workup (10), symptom control and patient satisfaction are high compared to medical therapy. This has previously been demonstrated in meta-analysis (11, 12).

From 1990-2000 the utilization of anti-reflux surgery in the USA rose to 16.7 procedures per 100.000 inhabitants with a concomitant rise in the use of the transabdominal laparoscopic approach. This resulted in a decline of perioperative mortality and morbidity (13, 14). The rate of anti-reflux surgery dropped to 6.1 procedures per 100.000 inhabitants in 2010, men the patients were now older with significantly higher levels of comorbidity. Despite this, length of stay, morbidity and mortality was reduced even further. The laparoscopic approach is used in 80% of American procedures and the rate has not changed during the last ten years. It is unknown whether Denmark follows the same trends, as the popularity of anti-reflux surgery has been somewhat limited and the surgical setup is different with significantly fewer centers.

Despite the high success rate of anti-reflux surgery, reoperation does occur. The indication for reoperation is most often recurrence of reflux symptoms or dysphagia, and reoperation should be preceded by thorough investigation and possible endoscopic balloon-dilation (15). Laparoscopic reoperation is both feasible and safe, but has been linked to higher morbidity, higher risk of conversion to open surgery and longer length of stay. The final result seem to result in less patient satisfaction than primary surgery, but the available evidence is limited by a high risk of bias due to small sample size and a possible underreporting of complications (16, 17).

An American study reported a cumulative five- and ten year incidence of reoperation of 5.2% and 6.9% respectively. The rate of reoperation was highest in the first year after primary anti-reflux surgery. 30% of reoperations were performed in a different center than the primary procedure. In a Danish study, Funch-Jensen et al (18), investigated rate of reoperation in Denmark 1997-2005 and calculated a rate of 5% without significant differences in length of stay, rate of complications or mortality compared to primary

surgery. Reoperation was however associated with a higher rate of conversion to open surgery with a tendency towards higher rates of conversion in low-volume centers. As in the American study, reoperation was often performed at different centers than the primary procedure. Whether this was the result of centralization or patient's wishes is unknown.

It is our hypothesis, that from 2000-2017, reoperative anti-reflux surgery was performed primarily with a laparoscopic approach without increased length of stay or rate of complications compared to primary surgery. Due to increased surgical experience the rate of complications is decreasing despite increased comorbidity. Endoscopic balloon-dilatation delays reoperation but does not prevent it.

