## Methods

The study is a two-part register-based cohort study based on data from The National Patient Registry, The Civic Registry and Danish Anaesthesia Database in the period 1996-2017. The two individual parts of the study concerns the same population.

The population is defined as all adult Danish patients undergoing anti-reflux surgery (Nomesco: KJBC00, KJBC01, KJBC02, KJBW96, KJBW97) from 2000-2017 identified from The National Patient Register.

Age, sex, Charlson Comorbidity Index at date of surgery and length of stay in relation to any surgery and any surgical or endoscopic procedure performed after anti-reflux surgery (including diagnosis 30 days postoperatively to establish possible morbidity) are derived from the National Patient Registry.

ASA-score, weight, height, use of alcohol or tobacco and priority of any surgery (emergency or planned) during the study period are retrieved from The Danish Anaesthesia Database. From the Civic Register, data on mortality in the study period are retrieved.

Information on the use of pharmacological treatment for gastroesophageal reflux disease on population level is retrieved from MEDSTAT and data on population size on population level are retrieved from Statistics Denmark.

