## Statistical analysis

### 1) Course of illness leading to reoperative anti-reflux surgery

Data will be analyzed using STATA15. Descriptive analysis of age, sex, comorbidity (Charlson Comorbidity Index, ASA-score, BMI, alcohol/tobacco use), complications to surgery, rate of endoscopic dilation and mortality comparing patients with only primary anti-reflux surgery and patients with reoperation during the study period, will be performed using Student's t-test, Chi2-test and Mann-Whitney-U test.

Logistic regression will be performed with reoperation (laparoscopic, open or other) as primary outcome and age, sex, comorbidity (Charlson Comorbidity Index, ASA-score, BMI, alcohol/tobacco use), complications to surgery and endoscopic or surgical procedure during study period as independent variables. If the number of patients is sufficient, subanalysis will be performed with emergency reoperation as dependent variable/outcome.

Secondary analysis will be performed using Cox-regression investigating time to reoperation with age, sex, comorbidity (Charlson Comorbidity Index, ASA-score, BMI, alcohol/tobacco use), complications to surgery and endoscopic or surgical procedure during study period as independent variables.

*2) Utilization of treatment of gastroesophageal reflux disease.*

The rate of anti-reflux surgery per 100.000 inhabitants for each year during the study period will be calculated using census data from Statistics Denmark. From MEDSAT the rate of use of pharmacological anti-reflux treatment per 100.000 inhabitants will be calculated using abovementioned census-data. Trends in the utilization of surgery are investigated with trend-analysis in the form of Poisson-regression alternatively negative binominal regression.

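### The plan hypothesises no increase in length of stay or complications after redo surgery, but no planned analysis can support that claim: complications get only a test of difference and length of stay gets no analysis

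*Combined protocol and SAP*

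**What the plan says.** The last paragraph of the Background lists several hypotheses without ranking them. One is that reoperations were performed "without increased length of stay or rate of complications compared to primary surgery".

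Under Statistical analysis, part 1, the group comparison is called descriptive and "will be performed using Student's t-test, Chi2-test and Mann-Whitney-U test". Its contrast is at patient level: "comparing patients with only primary anti-reflux surgery and patients with reoperation during the study period". The variables listed are age, sex, comorbidity, "complications to surgery, rate of endoscopic dilation and mortality". Length of stay is not among them, although Methods extracts "length of stay in relation to any surgery".

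The models run in another direction: "Logistic regression will be performed with reoperation (laparoscopic, open or other) as primary outcome". The Cox model takes time to reoperation as its outcome. In both, complications are an explanatory variable.

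The document gives no sample size, power, significance level, margin or confidence-interval criterion, and no rule for interpreting a non-significant result.

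**The concern.** A hypothesis of no increase is of non-inferiority type. The t, Chi2 and Mann-Whitney tests take equality as the null hypothesis. They can produce evidence of a difference, but failing to reject is not evidence of its absence, least of all when one group is small. The Background's own figures put reoperation at about 5 to 6.9%.

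A real increase is also plausible on the protocol's own account, since laparoscopic reoperation "has been linked to higher morbidity, higher risk of conversion to open surgery and longer length of stay". The Background adds that this evidence suffers from small samples and possible underreporting of complications. What is at stake is whether the study can say anything reliable about the safety of redo relative to primary surgery.

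**Working it through.** **Hypothesis against analysis**

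| Element | Hypothesis (Background) | Analysis (part 1) |
|---|---|---|
| Unit | redo operation vs primary operation | patients with primary surgery only vs reoperated patients |
| Complications | not increased | test of difference; covariate in both models |
| Length of stay | not increased | none |
| Criterion | none | none |

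Part 1 does not say which operation a reoperated patient's complications belong to. If they are those of the primary operation, the test does not address the hypothesis at all.

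**Inputs for the size of the problem.** The plan has no figure of its own to reproduce. From the Background: redo share 5% (earlier Danish study) and 6.9% (ten-year incidence, American study). Assumed, because the document gives neither: 2,000 to 8,000 primary operations, and a complication rate after primary surgery of 4% or 8%. Redos then run from 0.05 × 2,000 = 100 to 0.069 × 8,000 = 552.

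**Power of the two-sided 5% Chi2 test**, treating the operations as independent. Here n1 is primary operations, n2 redos, d = p2 − p1, and p̄ is the pooled rate:

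s0 = √[p̄(1−p̄)(1/n1+1/n2)], s1 = √[p1(1−p1)/n1 + p2(1−p2)/n2]

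power = Φ((d − 1.96 s0)/s1) + Φ((−d − 1.96 s0)/s1)

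Low end, 4% to 6%:
- p̄ = (80+6)/2,100 = 0.04095, s0 = 0.02031, s1 = 0.02415.
- Power = Φ(−0.82) + Φ(−2.48) = 0.206 + 0.007 = 0.21.

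High end, 4% to 6%:
- p̄ = (320+33.12)/8,552 = 0.04129, s0 = 0.00876, s1 = 0.01034.
- Power = Φ(0.27) = 0.61; the second term is negligible.

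| Primary / redo | 4%→6% | 4%→8% | 8%→12% | 8%→16% |
|---|---|---|---|---|
| 2,000 / 100 | 21% | 50% | 33% | 74% |
| 8,000 / 552 | 61% | 97% | 87% | 100% |

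At a 4% base rate, a true 1.5-fold increase would therefore give a non-significant result in 39 to 79% of such studies.

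**Precision if the rates are equal at 4%.** The 95% half-width is 1.96 √[0.04 × 0.96 × (1/n1+1/n2)]. This is 3.9 percentage points with 100 redos and 1.7 with 552. At the low end the interval reaches 4 + 3.9 = 7.9%, so it cannot exclude a near doubling.

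**What a margin would require** (one-sided 2.5%, 80% power, no true difference): redos ≈ (1.96+0.84)² p(1−p)(1+k)/m², where k is the ratio of redo to primary and m the margin. At an assumed 5% rate, with redos 5 to 6.9% of the total:
- a 3-point margin needs about 437 to 445 redos;
- a 5-point margin needs about 157 to 161.

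For length of stay, a margin of 0.2 standard deviations needs about 207 to 211. These margins only illustrate the scale.

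**The case against.** The strongest reply is that the comparison is labelled descriptive, that the only outcome named as primary is reoperation, and that the document nowhere says a non-significant test will count as confirmation. All of this is correct. A reader might infer that the plan would declare redo surgery safe whenever precision is poor. The Background makes that plausible, because it reports the earlier Danish study through its lack of significant differences and then states a no-increase hypothesis. But the plan contains no such decision rule, so this remains a risk of misreading.

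Three other inferences also go too far:
- **That this is the main hypothesis.** It is one of several unranked statements.
- **That length of stay would be judged by the t-test or the Mann-Whitney test.** It is not on the list of variables compared; the gap there is a missing analysis.
- **That redos will be too few for the test to be informative.** No count is given, and at the upper end of the assumed range a doubling would almost always be detected.

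It can also be said that a register study of all eligible patients needs no formal margin. That stands: estimation with an interval would be enough. What does not fall away is that a stated hypothesis has no analysis capable of supporting it, whatever the cohort size.

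**Conclusion.** The point holds, as something that should be fixed. No result of the planned analyses could support the no-increase hypothesis: complications have only a test of difference on a patient-level contrast, length of stay has no analysis, and no margin or interval criterion exists. This does not depend on any assumed number.

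The size does depend on assumptions. With 2,000 to 8,000 primary operations and the Background's 5 to 6.9% redo share, power against a 1.5-fold increase is about 21-61% at a 4% base rate and 33-87% at 8%. Against a doubling it is 50-97% and 74-100%. Moderate increases could thus easily be missed over much of the range, whereas large ones would often be found. The planned regressions on reoperation are not affected, and so the point does not undermine the primary analysis.

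**What to change.** In Statistical analysis, part 1:

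1. Add a procedure-level comparison of redo with primary operations for 30-day complications (risk difference or ratio) and for length of stay (ratio or difference of means).
2. Report two-sided 95% confidence intervals that allow for patients contributing both operations, for example cluster-robust standard errors by patient.
3. State that p>0.05 is not support for the hypothesis.
4. Choose one of two routes. Either fix a margin for each outcome before data extraction and conclude that there is no increase only if the upper confidence limit lies below it; or reword the hypothesis as estimation and report the size of increase that the interval excludes.

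The cost is a wording change, a little more analysis and, on the first route, a decision on margins. Length of stay and postoperative diagnoses are already in the extraction described under Methods. The downside is that the result may have to be reported as inconclusive.

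### The causal hypothesis about balloon-dilatation has no analysis that can answer it: the whole-cohort models are confounded by indication, and the net direction of bias cannot be predicted

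*Combined protocol and SAP*

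**What the plan says.** The hypothesis at the end of the Background is "Endoscopic balloon-dilatation delays reoperation but does not prevent it". The same section states that "The indication for reoperation is most often recurrence of reflux symptoms or dysphagia" and that "reoperation should be preceded by thorough investigation and possible endoscopic balloon-dilation". On the protocol's own account, then, dysphagia leads to reoperation and dilatation is a possible step on the way.

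Methods sets no symptom restriction: "The population is defined as all adult Danish patients undergoing anti-reflux surgery". Diagnoses are mentioned there in one parenthesis, "including diagnosis 30 days postoperatively to establish possible morbidity". Dysphagia is not a listed variable.

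In part 1 of the Statistical analysis, dilatation is named only in the unadjusted descriptive comparison: "rate of endoscopic dilation and mortality comparing patients with only primary anti-reflux surgery and patients with reoperation during the study period". The logistic and Cox models list age, sex, comorbidity, and then "complications to surgery and endoscopic or surgical procedure during study period as independent variables". Dilatation has no term of its own, no time-dependent coding is stated, and no indication for the procedure enters either model.

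**The concern.** Delaying and preventing are effects of dilatation on patients who could have been dilated. The models as written would compare patients who had a procedure with everyone who did not. Having been dilated marks a patient who probably already has a symptom that leads to reoperation. Part of the estimate is therefore the effect of having dysphagia.

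What is at stake is the interpretation. A ratio near or above 1 could be published as evidence that dilatation does not prevent reoperation when in truth it does. Time-dependent coding alone would not cure this, because the comparator would still include patients with no indication.

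**Working it through.** The plan gives no figure for this hypothesis (no effect size, dysphagia rate or dilatation rate), so there is nothing to reproduce. The check asks what the whole-cohort contrast would show if dilatation truly halved reoperation.

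**Inputs**
- Overall reoperation risk: 5.2% at five years and 6.9% at ten years (American study cited in the Background).
- Assumed: d, share with dysphagia (5–30%); f, share of those dilated (30–100%); k, reoperation risk in undilated dysphagia relative to no dysphagia (1.5 to 5); r = 0.5, true risk ratio for dilatation. Only patients with dysphagia are dilated.

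**Apparent risk ratio**

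With p the risk without dysphagia, dilated patients have risk r·k·p and undilated patients have [(1−d)p + d(1−f)kp]/(1−df). Hence

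apparent RR = r·k·(1−df) / [(1−d) + d(1−f)k].

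The overall risk cancels, so the ratios are the same at 5.2% and 6.9%. At d = 0.10, f = 0.50, r = 0.5:

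| k | Calculation | Apparent RR (true 0.5) |
|---|---|---|
| 1.5 | 0.7125/0.975 | 0.73 |
| 2 | 0.95/1.00 | 0.95 |
| 3 | 1.425/1.05 | 1.36 |
| 5 | 2.375/1.15 | 2.07 |

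At 5.2% overall, k = 3 corresponds to 6.9% versus 5.1%, and k = 5 to 10.2% versus 4.9%. Odds ratios are close to these (1.38 and 2.19). Over d = 5–30% and f = 50–80%, k = 3 gives 1.11 to 1.47 and k = 5 gives 1.47 to 2.40.

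**Where the sign changes**

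The apparent RR exceeds 1 when k > (1−d)/[0.5(1−df) − d(1−f)]. At d = 0.10, f = 0.50 this is 0.9/0.425 = 2.12. Over d = 5–30% and f = 30–100% it runs from 2.0 to 2.9. Put another way, undilated patients with dysphagia must have more than twice the cohort's average risk: 2 × 5.2% = 10.4% at five years, or 2 × 6.9% = 13.8% at ten.

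**Timing**

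A patient must remain free of reoperation until the dilatation in order to count as dilated first. Fixed coding credits that event-free time to dilatation, which lowers its hazard ratio. A simulation (60,000 patients, five years, constant hazards, true hazard ratio 0.5, d = 10%, f = 50%, one run per row) gave these hazard ratios:

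| k | Mean time to dilatation | Fixed, whole cohort | Time-dependent, whole cohort | Time-dependent, dysphagia only |
|---|---|---|---|---|
| 1.5 | 0.5 years | 0.62 | 0.70 | 0.50 |
| 2 | 0.5 years | 0.82 | 0.92 | 0.48 |
| 3 | 0.5 years | 1.35 | 1.52 | 0.60 |
| 3 | 2 years | 0.87 | 1.27 | 0.48 |
| 5 | 0.5 years | 1.88 | 2.13 | 0.53 |
| 5 | 2 years | 1.34 | 2.03 | 0.55 |

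Two further scenarios with f = 80% fit the same pattern. Across all eight, the restricted analysis gave 0.47 to 0.60. That is a best case: it assumes dysphagia is fully recorded and that dilatation is unrelated to severity among those who have it.

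**The case against.** A reader might infer that the plan will make dilatation look harmful whatever the truth. The documents do not support that.

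- Below roughly a doubling of risk with dysphagia, a true halving still looks protective, only understated.
- A strong enough effect shows through even at high risk. Take 5% dysphagia, half dilated, 15% risk in undilated dysphagia and a true ratio of 0.3. Dilated risk is 0.3 × 15% = 4.5%, undilated risk is (5.2% − 2.5% × 4.5%)/97.5% = 5.22%, and the ratio is 0.86.
- The procedure term is described as occurring during the study period and reads as fixed. Immortal time then pulls the other way and can reverse the sign (0.87 against 1.27 at k = 3 and a mean of two years to dilatation).

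Two other inferences are also too strong. That most undilated patients have no dysphagia is plausible given a reoperation risk of 5–7%, but no figure is given. That dysphagia at the time of dilatation is unavailable over-reads Methods: the 30-day parenthesis follows the mention of later procedures and may cover diagnoses around each of them.

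Some mitigation is possible. The complications covariate may absorb early coded dysphagia, and if procedures are entered by type, endoscopy may act as a partial symptom proxy. Neither is specified, and neither makes the comparison one among patients with the indication. Two opposing biases of unknown size do not recover the true effect.

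**Conclusion.** The concern holds in a conditional form. No planned analysis is set up for the dilatation hypothesis, and the nearest one, the procedure term in the whole-cohort models, is confounded by indication. Under the stated assumptions, a true halving is understated if dysphagia raises reoperation risk less than about 2-fold, and looks neutral or harmful once it raises it more than about 2- to 3-fold. Fixed coding adds a bias in the opposite direction, so the net sign cannot be predicted from the documents.

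The conclusion that neither delay nor non-prevention can be inferred rests on the protocol's own text. The sizes rest on assumed dysphagia rates, dilatation rates and symptom-specific risks.

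**What to change.** In part 1 of the Statistical analysis:

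1. Define dilatation as its own time-dependent exposure in the Cox model, separate from other endoscopic or surgical procedures. The logistic model cannot carry this timing and should not be used for the hypothesis.
2. Test the hypothesis among patients with a registered postoperative dysphagia or stenosis diagnosis, starting follow-up at the first such contact or endoscopy. Restricting to endoscoped patients alone is not enough, because those endoscoped but not dilated include patients with recurrent reflux, the other main indication for reoperation.
3. State how dilatation after the start of follow-up is handled, for example by counting a patient as undilated until the date of dilatation and as dilated from then on.
4. Add the contact diagnosis to the National Patient Registry extract if it is not already covered.
5. Report the whole-cohort result only as the risk of reoperation after dilatation, with no claim about delay or prevention. If the diagnosis field proves unusable, report only that association.

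The cost is revised analysis wording and possibly one more field from a registry already in use. The downsides are a smaller analysis set and residual confounding by severity and by incomplete diagnosis coding.

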## Methods

The study is a two-part register-based cohort study based on data from The National Patient Registry, The Civic Registry and Danish Anaesthesia Database in the period 1996-2017. The two individual parts of the study concerns the same population.

The population is defined as all adult Danish patients undergoing anti-reflux surgery (Nomesco: KJBC00, KJBC01, KJBC02, KJBW96, KJBW97) from 2000-2017 identified from The National Patient Register.

Age, sex, Charlson Comorbidity Index at date of surgery and length of stay in relation to any surgery and any surgical or endoscopic procedure performed after anti-reflux surgery (including diagnosis 30 days postoperatively to establish possible morbidity) are derived from the National Patient Registry.

ASA-score, weight, height, use of alcohol or tobacco and priority of any surgery (emergency or planned) during the study period are retrieved from The Danish Anaesthesia Database. From the Civic Register, data on mortality in the study period are retrieved.

Information on the use of pharmacological treatment for gastroesophageal reflux disease on population level is retrieved from MEDSTAT and data on population size on population level are retrieved from Statistics Denmark.

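### The lead logistic model codes death before reoperation as redo-free follow-up, so odds ratios for age and comorbidity, read as effects on the reoperation rate, are biased toward protective

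*Combined protocol and SAP*

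**What the plan says.** All points are in the combined protocol and SAP.

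- **Cohort (Methods).** Patients enter at anti-reflux surgery "from 2000-2017 identified from The National Patient Register". The register data also end in 2017, so potential follow-up runs from about 0 to 18 years.
- **Lead model (Statistical analysis, part 1).** "Logistic regression will be performed with reoperation (laparoscopic, open or other) as primary outcome". Age, sex, Charlson index, ASA-score and other factors are the independent variables. No time window, censoring date or rule for death is given.
- **Second model (same section).** "Secondary analysis will be performed using Cox-regression investigating time to reoperation", on the same covariates. No start or end of follow-up and no censoring rule is given.
- **Exit data (Methods).** "From the Civic Register, data on mortality in the study period are retrieved". Emigration is not listed.
- **Stated use of mortality (Statistical analysis, part 1).** It appears once, in the descriptive comparison: "rate of endoscopic dilation and mortality comparing patients with only primary anti-reflux surgery and patients with reoperation during the study period".

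**The concern.** A yes/no outcome over open-ended follow-up does not distinguish a patient who was observed for many years without a redo from one who died early and had little time to have one. A covariate that raises mortality shortens the time in which a redo can happen. It will then be associated with fewer reoperations even if it has no influence on the rate of reoperation among patients still alive.

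Age, Charlson index and ASA-score are among the risk factors under study, and all three can be expected to track death. Part 1 of the study concerns the course leading to reoperation, so readers will naturally take these odds ratios as effects on the tendency to need a redo. On that reading, the error runs in one direction for the covariates that matter most.

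**Working it through.** The plan states no sample size, power or target estimate, so there is no figure of its own to reproduce. The check asks what odds ratio the logistic model returns when the covariate has no effect on the reoperation rate.

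**Inputs from the document (Background).** Cumulative reoperation of 5.2% at five years and 6.9% at ten years in the cited American study, with the rate highest in the first year.

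**Assumptions, because the document gives no figures.** 2% reoperated in year 1; uniform entry over 18 years; the hazard of years 5-10 continued to year 18; the cited incidences taken as risks in the absence of death; death at 0.5% per year in the reference group and 1%, 2%, 5% or 10% in the comparison group.

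**Step 1: hazard h(t), per year.**
- Year 0-1: −ln(1 − 0.02) = 0.0202
- Years 1-5: (−ln(1 − 0.052) − 0.0202)/4 = (0.0534 − 0.0202)/4 = 0.0083
- After year 5: (−ln(1 − 0.069) − 0.0534)/5 = (0.0715 − 0.0534)/5 = 0.0036

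With no deaths this returns 5.20% at five years and 6.90% at ten.

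**Step 2: proportion coded as reoperated at death rate d.**

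P(d) = ∫₀¹⁸ h(t) · exp(−∫₀ᵗ (h + d)) · (1 − t/18) dt

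The hazard h is the same in both groups (true hazard ratio 1). OR = [P(d)/(1 − P(d))] / [P(0.005)/(1 − P(0.005))].

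| Deaths per year | Coded as reoperated | OR vs 0.5% | OR if the hazard is constant over years 0-5 |
|---|---|---|---|
| 0.5% | 6.08% | 1.00 | 1.00 |
| 1% | 5.97% | 0.98 | 0.98 |
| 2% | 5.76% | 0.94 | 0.94 |
| 5% | 5.22% | 0.85 | 0.83 |
| 10% | 4.52% | 0.73 | 0.70 |

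Example at 5%: (0.0522/0.9478)/(0.0608/0.9392) = 0.0551/0.0647 = 0.85.

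**Step 3: three analyses of the same simulated data** (400,000 patients, death at 5% vs 0.5% per year, true hazard ratio 1).
- Logistic regression: OR 0.85 (95% CI 0.83 to 0.87)
- Cox, censored at death: HR 1.00 (standard error of the log HR 0.013)
- Cox, with the dead kept at risk to the end of the study: HR 0.86

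**Step 4: a fixed window.** With complete five-year follow-up, the OR at 5% vs 0.5% is 0.89 to 0.91, depending on the shape of the hazard. A window reduces the distortion of the rate but does not remove it.

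**Step 5: unrecorded emigration in one group only** (assumed rates). At 0.1%, 0.5% and 1% per year, the apparent OR or HR is about 0.996, 0.98 and 0.96.

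**The case against.** The strongest reply is that counting the dead as not reoperated is not wrong in itself. A patient who dies without a redo truly never had one. The Aalen-Johansen estimator counts deaths that way, and so does a Fine-Gray model. With known administrative censoring, Fine-Gray keeps the dead in the risk set, which is the analysis that gave 0.86, close to the logistic 0.85. This stands. The odds ratio misleads about the rate of reoperation among the living, but a lower actual cumulative risk in patients who die sooner is real. The point therefore depends on which question is being answered, and the plan does not say.

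It is also fair that the mortality contrasts are assumed and that small ones give almost no bias. That limits the size of the effect, not its direction.

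Three stronger readings are tempting, and the document does not support them:

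- **The Cox model has the same fault.** Mortality over the study period is to be retrieved, so this model can censor at death. The plan leaves that unstated; nothing says the dead stay at risk.
- **Missing emigration makes older or sicker patients look protected.** Nothing in the document suggests that emigrants are older or sicker. If they are younger, the bias runs the other way, and its size is small in any case.
- **The hypothesis that "Endoscopic balloon-dilatation delays reoperation but does not prevent it" is undermined by deaths.** The document gives nothing linking dilatation to mortality, and for actual cumulative risk those who die are properly counted as not reoperated.

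**Conclusion.** The concern holds for the lead logistic model when its odds ratios for age, Charlson index and ASA-score are read as effects on the reoperation rate. With no true effect, the odds ratio is pulled to about 0.98, 0.94, 0.85 and 0.73 at assumed mortality of 1%, 2%, 5% and 10% per year against 0.5%, so the bias ranges from negligible to moderate. These figures rest on the cited 5.2% and 6.9%, uniform entry, an assumed hazard shape and assumed death rates.

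A reader might infer that older and sicker patients will necessarily appear protected. That follows only if the true effect is null or small; a truly harmful effect may merely be attenuated.

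For the Cox model the finding is only that its censoring is unspecified. Emigration is a minor gap: about 4% or less at assumed rates up to 1% per year, in an unknown direction.

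**What to change.** 1. Base the risk-factor conclusions on the Cox model as a cause-specific analysis, in place of the logistic model. Define follow-up as running from primary surgery to the first of reoperation, death, emigration or end of 2017.
2. Add the date of emigration to the Civic Register extract, and state that mortality is retrieved as a date.
3. Report Aalen-Johansen cumulative incidence of reoperation with death as a competing event. State that this describes actual cumulative risk, in which deaths are properly counted as not reoperated, and that it answers a different question from the hazard. A Fine-Gray model is optional.
4. If the logistic model is kept in a supporting role, give it a fixed window and say how deaths inside the window are handled.

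The cost is one or two extra date fields and a reordering of analyses already planned. The section on funding and ethical considerations places the data permissions before the start of the study, so at that stage the fields can still be requested.
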